
Dose and Mode of Administration
	
 • Three (3) capsules of LAU-7b (300 mg total dose) or matching placebo (randomization 1:1) will be administered in the fed state with the first meal of the day (morning if possible) for 6 consecutive cycles consisting of 21 days on treatment followed by a 7-day treatment-free period. • Study treatment will be administered on top of current Standard of Care therapies.

Statistical Analysis
	
Sample size: A minimum of 136 CF patients will be randomized in this study. Sample size calculation is based on the primary efficacy variable, FEV₁ % predicted (absolute change) and on the following assumptions:

- A t-test of the difference of the mean absolute change in FEV₁ of each group (active versus placebo) will be used;
- The FEV₁ (absolute change) data is normally distributed in each treatment group;
- The FEV₁ variance, expressed as the Standard Deviation (SD) is 8%;
- The FEV₁ clinical difference of interest (effect size) is 4%;
- The minimum statistical power of the t-test is 80% (0.8);

A minimum of 60 completed patients per group will be required to detect as significant a difference of 4% between fenretinide and placebo for FEV₁ % predicted (absolute change).

Primary Efficacy Endpoint Analysis:

In the analysis for the primary efficacy endpoint, change from baseline in FEV₁ % predicted (absolute change), including all measurements up to Week 28 (both during and after treatment measurements, including after treatment discontinuation) will be analyzed based on a mixed-effect repeated-measure model. Even though no imputations will be used in the primary analysis, a sensitivity analysis will be conducted where missing data points will be imputed using appropriate interpolation methods; extrapolation methods will be used for truncated FEV₁ % predicted values.

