2 SCHEDULE OF EVENTS

	Screening	Baseline	Telephone contacts	End-Of-Cycle 1	End-Of-Cycle 2 ¹	End-Of-Cycle 3	End-Of-Cycle 4 ¹	End-Of-Cycle 6	Follow-up (End-Of-Study visit)	Start of PEx Visit ²	End of PEx Visit ²
Day number	Days -28 to -1	Day 1	Days 10, 38, 66, 94, 122, 150	Day 21	Day 49	Day 77	Day 105	Day 161	Day 189 (or early termination)	1st day of IV Antibiotic	Last day of IV Antibiotic
Visit number	Visit 1	Visit 2	N/A	Visit 3	Visit 4	Visit 5	Visit 6	Visit 7	Visit 8	N/A	N/A
Verification of ID and age	X										
Informed consent	X										
Confirmation of CF diagnosis	X										
Inclusion/Exclusion criteria	X	X									
Medical History including detailed PEx history and precise dates	X	X									
Concomitant Meds and verification of disallowed medications	X	X	X	X	X	X	X	X			
Weight, Height (screening only) and Body Mass Index	X	X		X		X		X	X	X	X
Complete Physical Examination	X								X		
Focused Physical Examination		X		X		X		X			
Ophthalmological examination ³	X					X			X		
Night Vision Questionnaire	X			X		X		X	X		
Pulmonary Function Testing (at min. FEV1)	X	X		X	X	X	X	X	X	X	X
12-Lead ECG	X			X		X		X	X		
Vital Signs including respiratory rate, oxygen saturation and temperature	X	X		X		X		X	X		
Hematology ⁴	X	X		X	X	X	X	X	X		
Chemistry ⁵	X	X		X	X	X	X	X	X		
Pregnancy Test for women	X (serum)	X (urine)		X (urine)	X (urine)	X (urine)	X (urine)	X (urine)	X (urine)		
Urinalysis ⁶	X	X		X	X	X	X	X	X		
Sputum ⁷	X					X		X			
Cystic Fibrosis Questionnaire-Revised (CFQ-R)		X				X		X	X		
Matouk Disease Score (at selected sites)		X				X		X	X		

	Screening	Baseline	Telephone contacts	End-Of-Cycle 1	End-Of-Cycle 2 ¹	End-Of-Cycle 3	End-Of-Cycle 4 ¹	End-Of-Cycle 6	Follow-up (End-Of-Study visit)	Start of PEx Visit ²	End of PEx Visit ²
Day number	Days -28 to -1	Day 1	Days 10, 38, 66, 94, 122, 150	Day 21	Day 49	Day 77	Day 105	Day 161	Day 189 (or early termination)	1st day of IV Antibiotic	Last day of IV Antibiotic
Visit number	Visit 1	Visit 2	N/A	Visit 3	Visit 4	Visit 5	Visit 6	Visit 7	Visit 8	N/A	N/A
Lipidomics (AA, DHA, EPA)		X		X				X	X		
Inflammation and oxidative stress markers, ceramides and metabolipidomic markers		X		X				X			
Systemic bone formation/resorption biomarkers (all patients)		X						X			
Lumbar spine bone density (first 24 patients at selected sites)		X							X		
Randomization		X									
Supervised dosing		X									
Dispensing of study drug packs and drug compliance check where applicable		X		X		X					

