Reporting of PEx by patients		X	X	X	X	X	X	X	X	X	X
PEx-related biomarkers in Plasma ⁸										X	X
Plasma retinol and RBP ⁹	X	X		X		X		X	X		
Plasma sample for fenretinide C _{min}				X ¹⁰				X ¹⁰			
Adverse Events		X	X	X	X	X	X	X	X	X	X

¹ The Days 49 and 105 visits are simplified visits focused on safety

² Only for patients experiencing episodes of PEx with need for IV antibiotic (as decided by the treating physician)

³ Complete ophthalmological examination: visual acuity, examination for amblyopia, examination of eyelids, conjunctiva, cornea, pupillary reactions to light and accommodation, specific dark adaptation tests, low contrast visual function, lens, vitreous humor, fundus examination of retina and retinal vessels, fundus visualization of optic nerve and macula. If clinically indicated by the ophthalmologist, an electroretinogram will also be performed

⁴ Hematology: CBC, hemoglobin, hematocrit, differentials (absolute and %) and platelets

⁵ Chemistry: creatinine, BUN, total bilirubin, alkaline phosphatase, AST, ALT, GGT, total protein, Na, K, Ca, bicarbonate, phosphate, albumin, glucose, total cholesterol, LDL cholesterol, HDL cholesterol and triglycerides

⁶ Urinalysis: Includes appearance, pH, specific gravity, protein, hemoglobin, urobilinogen, ketones, bilirubin, nitrites, leucocyte esterase and leukocytes

⁷ Sputum: Sputum will be induced with hypertonic saline according to a standardized procedure across sites. Samples will serve for the assessment of presence and/or density of PsA by CFU determination

⁸ Blood sampling for select biomarkers in plasma (such as AA, DHA, EPA, interleukin-1 receptor antagonist (IL-1ra), IL-6, IL-8, IL-10, G-CSF, calprotectin, absolute neutrophils count, ceruloplasmin, haptoglobin, NEAPC, SAA, and hsCRP).

⁹ Plasma retinol and Retinol Binding Protein will be measured for exploratory correlation with the ophthalmological assessments

¹⁰ Blood sampling for C_{min}: Blood samples will be obtained from all patients pre-dose on Days 21 and 161; Blood will be drawn using BD Vacutainer™ spray coated K2 EDTA tubes. Plasma will be harvested and assayed for fenretinide, its active metabolite (4-MPR) and 4-oxo-fenretinide by a validated LC/MS/MS method.

TABLE OF CONTENT

1	SYNOPSIS.....	4
2	SCHEDULE OF EVENTS	10
3	GLOSSARY OF TERMS AND ABBREVIATIONS	16
4	STUDY PERSONNEL	18
5	INTRODUCTION.....	19
5.1	Investigational product.....	19
5.1.1	Rationale for LAU-7b, a novel and improved oral formulation of fenretinide.....	19

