Fenretinide has been safely administered in chemoprevention trials up to dose of 300 mg per day (1-1.5 μM plasma levels) for prolonged periods of time from 6 months to 5 years in large cancer populations with no significant toxicity^{69, 77, 78, 79, 80, 81}. Mild grade of nyctalopia and dermatologic disorders (dry skin, pruritus) were the most common side-effects of fenretinide treatment; rate of occurrence of both types of events tended to decrease with time or to recover spontaneously during the treatment period or shortly after cessation of dosing. Fenretinide plasma concentration (12 h post dose) at steady state was estimated to be $\sim 1 \mu\text{M}$ at 200mg dose and $\sim 1.5 \mu\text{M}$ at 300 mg dose. Adverse effects typical of other retinoids, such as decreased bone density, ligament calcification, and skeletal hyperostosis were not observed in these studies. Even after five years of therapy, abnormalities in night vision improved significantly after 7 days off therapy, and completely resolved one month after stopping fenretinide; plasma retinol concentrations returned to normal in one month following discontinuation of fenretinide^{80, 81}.

Single and repeat daily dose PK studies with fenretinide softgel formulation in healthy subjects and patient population indicate that fenretinide plasma exposure (C_{max} , AUC) also increased upon repeat daily dosing to reach a steady state level at 4-5 days^{82, 74, 83}. Presence of food increased significantly the plasma levels of the drug and has been used since as standard recommendation for fenretinide dosing⁷⁴. The increase in exposure was dose proportional up to 800mg. Plasma exposure on Day 21 with 300mg/day dose of LAU-7b formulation in adult CF patients was approximately equivalent to the exposure at the dose of 800mg on Day 28 in healthy adults with the softgel formulation, indicating an increase in fenretinide bioavailability by a factor of >2 with LAU-7b.

High-dose clinical trials

Phase I trials of high-dose (up to 14.5 μM plasma levels) oral fenretinide in pediatric solid tumors have been conducted with the corn-oil softgel formulation^{76, 79, 84}.

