In two Phase I studies in children with neuroblastoma, fenretinide was given up to the dose of 4000 mg/m²/day over 28 days (3-6 patients/dose level), followed by a 7-day interruption, for a period of 6-25 courses without dose-limiting (DLT) toxicity^{76, 84}. Fenretinide pharmacokinetics was linear in the dose range 100–1,700 mg/m². Steady state peak plasma concentrations between 1.3 μM at 100mg/m² and 14.5 μM at 4000mg/m² were observed in the first course of treatment on Day 28. Similar to what has been observed in adult patients, cutaneous toxicity (dry skin and lips) and nyctalopia (Grade 1-2) were the most common adverse effects observed at most dose levels which rapidly reversed during the 7-day drug-free intervals and did not appear to be dose related. Grade 2 toxicities included skin xerosis (6 cases), hepatic toxicity (1 case),

diarrhea (1 case), nyctalopia (3 cases), and headache (1 case). Nyctalopia of grade 3 occurred in one patient with the 1000mg/m² dose. None of the patients discontinued the drug because of toxicity. The maximum tolerated dose was not reached in these studies; however, they were terminated due to difficulties with patient compliance in consuming the required number of corn-oil based softgel capsules.

In a study in 54 children (2-20 years old) with high-risk solid tumors conducted by the Children's Cancer Group "CCG", a maximum tolerated dose (MTD) of oral fenretinide, divided BID - TID, given for 7 days, every 3 weeks, was defined as 2475 mg/m²/day, which achieved fenretinide peak plasma levels of 9.9 ± 5 µM with minimal systemic toxicity⁷⁹. Increased steady-state fenretinide levels were seen by Day 7 of therapy. Plasma retinol levels were decreased on Day 1 at all levels, and further decreased to an average of 33% of baseline by Day 7, with recovery to 55-106% of baseline by Day 21 (start of next course).

In all these high-dose pediatric studies, a wide range of peak plasma concentrations were observed at a given dose. It is possible that the differences of tolerability observed in these two studies (MTD achieved vs. no DLT observed) was dose-schedule dependent (i.e., TID vs. QD).

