9.2.4 Telephone contacts (around Days 10, 38, 66, 94, 122 and 150)

All patients will be contacted by phone on or about 10 days post-first dose of each cycle, to inquire about potential adverse events. Specific attention will be put on probing about adverse events related to visual disturbances or dermatological problems as follows: "How is your vision since the last visit/phone call?" and "How is your skin since the last visit/phone call?" Actions may be taken if necessary.

9.2.5 End-of-Cycle Visits (Visits 4, 5, 6 and 7, on Days 21(window: Days 21-22), 49(window: Days 49-51), 77(window: Days 77-79), 105 (window: Days 105-107) and 161(window: Days 161-163)

Special attention will be put on reports of symptoms/signs of pulmonary exacerbation by patients as this may trigger a set of additional assessments. Details are presented in Section 9.3 "Pulmonary Exacerbation Reporting and Evaluation". Adverse events will be monitored and captured at all visits.

1. **On Days 21, 77 and 161 visits**, the following assessments will also be done:
 - a. Focused physical examination;
 - b. Ophthalmological evaluation: The NVQ will be self-administered, and if Grade 2 severity criteria is met or exceeded (On Day 77 visit, the ophthalmological examination is planned, independently of the NVQ result), a full ophthalmological examination will be performed (includes dark adaptation tests), and if clinically indicated by the ophthalmologist, an electroretinogram will also be performed, in order to evaluate any potential ophthalmological condition developed during the treatment cycle);
 - c. Vital signs and 12-lead ECG;
 - d. Pulmonary function tests (FEV₁);
 - e. Pre-dose blood sampling and urine collection for safety laboratory tests, pregnancy test if applicable, plasma retinol and retinol-binding protein;
 - f. Study drug compliance check and concomitant medications;
 - g. Body weight, with BMI calculated.
2. **On Days 49 and 105 visits**, the following assessments will also be done;
 - a. Safety laboratory tests;
 - b. Pulmonary function test (FEV₁);
 - c. Concomitant medications.
3. **On Days 21 and 77 visits only**: All patients will return prior treatment boxes, for accountability purposes and will receive re-supply of study treatment for their next treatment cycle(s);

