Question 3. Recovery after dazzling: When you transition from a semi-obscure environment to a strongly lit one, do you remain dazzled?

Questions Q1 and Q2: Y (Yes) means normal. Questions Q3: N (No) means normal.

Assessment of the extent of reported symptoms: Level 0: no abnormal answer; Level 1: one abnormal answer; Level 2: two abnormal answers; and Level 3: three abnormal answers.

NVQ administration: Screening, Day 21, Day 77, Day 161, Day 189.

Level 1 NVQ will result in the given symptom to be considered a Grade 1 AE. However, it will not trigger an escalation to Step 2. Level 2 or 3 NVQ will automatically trigger a complete ophthalmological examination (Step 2) and its AE severity graded by the ophthalmologist.

Step 2: Complete ophthalmological examination, including specific dark adaptation tests

Administration: Screening, Day 77 and Day 189, and following any Level 2-3 NVQ report.

Suggested dark adaptation test to be included: a test able to evaluate dark-adaptation changes such as cone-rod break and the final rod threshold (see note below). Severity grading using CTCAE to be performed on confirmed nyctalopia episodes. If the reported symptoms do not get confirmed by the objective measures in Step 2, the default CTCAE severity Grade 1 will be used.

Step 3: Electroretinogram (ERG)

Administration: to be performed only if clinically indicated, in particular if the ophthalmological examination results are equivocal, or the type of signs/symptoms requires it.

Ophthalmologic examinations will be performed by (or under the oversight of) a licensed ophthalmologist at screening, Day 77 and Day 189 visits. It can also be triggered on demand if a patient reports signs of ophthalmologic nature upon questioning or at the time of the scheduled ophthalmologic questions posed on several occasions, according to the Schedule of Events, page 10.

The scheduled complete ophthalmologic examination will consist of the following: Examination of visual acuity, examination for amblyopia, examination of eyelids, conjunctiva, cornea, pupillary reactions to light and accommodation, low contrast visual function (Contrast Sensitivity), specific dark adaptation testsⁱⁱⁱ, lens,

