3.10 Ophthalmologic Examinations and Night Vision Questionnaire

The answers to the NVQ questionnaires and the resulting levels will be summarized by treatment group. The results (normal/abnormal, new adverse findings) of the planned during- and post-study ophthalmologic examinations will be presented, alongside the baseline examination and summarized by treatment group. Ad-hoc examinations and findings will also be presented alongside the baseline examination. All reported symptoms of nyctalopia and hemeralopia will be tabulated by treatment group. Reported symptoms confirmed by objective measures will be tabulated separately by treatment group. Individual data will be presented in listings.

No statistical analyses of ophthalmologic data are planned

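### After Day 77 the only scheduled objective eye examination is 28 days off drug, so objective confirmation of reversible night blindness in cycles 4 to 6 depends on symptom-triggered examinations that have no time limit

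*Protocol*

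**What the plan says.** Treatment is given for "6 consecutive cycles consisting of 21 days on treatment followed by a 7-day treatment-free period" (Protocol 1, Synopsis). The Schedule of Events marks the "Ophthalmological examination" at Screening, Day 77 and Day 189. Protocol 11.5 gives the same plan for the complete examination with dark-adaptation tests: "Administration: Screening, Day 77 and Day 189, and following any Level 2-3 NVQ report".

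On reversibility, Protocol 5.4.4.2 reports from the long-term chemoprevention trials that "abnormalities in night vision improved significantly after 7 days off therapy, and completely resolved one month after stopping fenretinide". It says of skin toxicity and nyctalopia in the paediatric high-dose trials that they were effects "which rapidly reversed during the 7-day drug-free intervals".

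The Night Vision Questionnaire is given at Screening and on Days 21, 77, 161 and 189. Two or three abnormal answers trigger a complete examination. Protocol 9.2.5 states the purpose of that examination: "in order to evaluate any potential ophthalmological condition developed during the treatment cycle". Neither 9.2.5 nor 11.5 says how soon it must be done. Under 11.5, a symptom that the objective tests do not confirm is graded CTCAE 1 by default.

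SAP 3.10 tabulates questionnaire answers and levels, examination results during and after the study, ad-hoc examinations, and all reported nyctalopia and hemeralopia. It adds: "Reported symptoms confirmed by objective measures will be tabulated separately by treatment group". It does not mention the time between the last dose and an examination.

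**The concern.** Reversible night blindness is the expected ocular effect of this drug, and an examination off drug is poorly placed to find it. The gap falls on the exposure that is new. Phase Ib gave three 21-day cycles, with drug-free periods averaging 57 and 27 days (Protocol 5.4.5.2). This trial gives six cycles with 7-day breaks, and Protocol 7.1.2 cites the longer treatment as a reason for making safety co-primary. The same section promises particular attention to objective investigation of nyctalopia symptoms.

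Two outputs are exposed. The confirmed-symptom table can be too low for late cycles. Severity can also be too low, because the default Grade 1 carries into the summary of adverse events by maximal severity (SAP 3.18). Lack of confirmation is already used as evidence in this programme: Protocol 5.4.5.2 supports the Phase Ib safety profile partly by noting that reported nyctalopia was not confirmed on examination.

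**Working it through.** This is calendar arithmetic. Power, alpha and dropout play no part.

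**Inputs.** Six cycles of 21 days on and 7 off (Protocol 1). Day 161 is a dosing day, since "Blood samples will be obtained from all patients pre-dose on Days 21 and 161" (Protocol 2, footnote 10). Examination and questionnaire days are from Protocol 11.5, telephone contacts from 9.2.4, clinic visits from the Schedule of Events.

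**Formula.** Cycle k starts on Day 1 + 28(k − 1), and its last dose is 20 days later.

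| Cycle | Dosing days | Scheduled examination | Questionnaire | Telephone vision question | Clinic visit |
|---|---|---|---|---|---|
| 1 | 1–21 | none | 21 | 10 | 21 |
| 2 | 29–49 | none | none | 38 | 49 |
| 3 | 57–77 | 77 | 77 | 66 | 77 |
| 4 | 85–105 | none | none | 94 | 105 |
| 5 | 113–133 | none | none | 122 | none |
| 6 | 141–161 | none | 161 | 150 | 161 |

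**The plan's own figure.** SAP 2.5 puts the End-of-Study visit 4 weeks after the last dose. 189 − 161 = 28 days = 4 weeks, so it reproduces.

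**Gap between scheduled examinations.** 189 − 77 = 112 days. These contain 3 × 21 = 63 dosing days, out of 6 × 21 = 126 planned.

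**Drug status at Day 189.** Protocol 5.4.5.1 expects fenretinide and its metabolites to be undetectable 7 to 10 days after the last dose. Day 189 is well beyond that.

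**Triggered examinations.** Timing depends on the source of the trigger.

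- Telephone contacts on Days 94, 122 and 150 fall on day 10 of cycles 4, 5 and 6 (94 − 85 + 1 = 10, and likewise for the others). Eleven dosing days remain (105 − 94 = 11), so an examination they prompt can be on drug.
- The Day 21 and Day 161 questionnaires fall on the last dosing day of a cycle. An examination not done at that visit falls in the 7-day break after cycle 1 or in the follow-up after cycle 6.
- Day 77 does not have this problem, because an examination is planned there whatever the questionnaire shows.

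**Why visit labels are not enough.** Under Protocol 8.4, a patient who stops treatment for a safety reason either stays on the visit schedule or attends at least one visit four weeks after the last dose. Someone who stops before Day 77 and stays on schedule has an off-drug Day 77 examination.

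**The case against.** The strongest reply is that the eye data for cycles 4 to 6 are not silent. Vision is asked about by telephone in each cycle. The questionnaire and plasma retinol and retinol-binding protein are taken on Day 161, a dosing day. One abnormal answer is already a Grade 1 adverse event, and on-demand examinations are allowed. SAP 3.10 tabulates every reported symptom, confirmed or not, and SAP 3.18 counts nyctalopia as a treatment-emergent event. All of this stands. A reader might infer that the eye tables will look clean whatever happens in the late cycles. The documents do not support that, because symptoms and questionnaire levels would still show it.

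Second, Day 189 is already treated as post-study, and Protocol 5.4.5.1 says follow-up is mostly drug-free. The examination covers retina, optic nerve, lens and contrast sensitivity, so it can show lasting damage. This also stands: Day 189 is uninformative only about effects that reverse.

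Third, 9.2.5 lists the triggered examination among the assessments of the Day 21, 77 and 161 visits, so delay is not certain. Moreover, 5.4.4.2 says abnormalities had improved at 7 days, not that they were gone. That is fair. What remains is that no limit is written and that an ophthalmologist must perform or oversee the examination.

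Finally, the mock tables are not in the available text, so the point about time since dose rests on the wording of SAP 3.10. The planned individual listings may allow the interval to be worked out patient by patient, but that does not change the summary tables.

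**Conclusion.** The concern holds in a limited form. After Day 77 no objective examination is scheduled on drug, over 63 of the 126 planned dosing days. The one scheduled examination that remains is 28 days after the last dose. Objective detection of reversible night blindness in cycles 4 to 6 therefore depends on a reported symptom leading to a timely examination. The confirmed-symptom table and nyctalopia severity can be understated for these cycles, and deficits that a patient does not report can be missed. By how much cannot be calculated from the documents, which give neither a late-cycle symptom rate nor a typical delay to examination.

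A reader might also want to put an upper confidence limit on ocular toxicity from a normal Day 189 table. The plan offers no basis for it: SAP 3.10 plans no statistical analysis of the eye data, and such a limit would describe only the off-drug state.

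The conclusion assumes that the reversibility in 5.4.4.2 carries over. Those data come from earlier trials of another formulation in other populations, and one month is slightly longer than 28 days.

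**What to change.** In SAP 3.10:

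- Derive days since last dose for every scheduled, triggered and ad-hoc examination.
- Present examination results and symptom confirmation in two groups: examinations on a dosing day or within the end-of-cycle windows of Protocol 9.2.5 (Days 21–22, 49–51, 77–79, 105–107 and 161–163), and examinations done off drug. In patients who had already stopped treatment, actual days since last dose takes precedence over the visit label.
- Report a symptom examined only off drug as *not assessed on drug*, not as unconfirmed.
- Describe Day 189 results as off-drug persistence or reversibility.

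Separately, the sponsor should reconcile the timing of triggered examinations in Protocol 9.2.5 and 11.5 with the purpose stated in 9.2.5 and the recovery described in 5.4.4.2. No particular visit or clinical rule is proposed here.

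The cost is SAP wording and one derived variable. Dose and interruption dates are already needed for the exposure and compliance calculations (SAP 3.5 and 3.12). The drawback is smaller denominators for the confirmed/not-confirmed split.
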